2.3 Secondary Objective(s) and Endpoint(s)

[figure not shown]
Secondary Objective	Endpoint(s)	Time Frame
1. To evaluate the impact of TXA on patient and provider rating of bruising, comparing the TXA side to the control side	
Ecchymosis will be compared between the right and left side at each post operative visit and documented. The observer will be blinded to the laterality of TXA	From application in the operating room to 30 days of follow up
2. To evaluate the impact of TXA on total drain output in the first post operative day	
Total drain output over the life of the drain, compared between control and study groups	From drain placement in the operating room to discharge on POD1
3. To evaluate the impact of TXA on total drain duration	
Total drain duration compared between control and study groups	From drain placement in the operating room to removal of the drain

3 Study Design

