3.1 Characteristics

We propose a prospective, placebo-control trial looking at the effect of topical tranexamic acid on post-operative bleeding, hematoma, seroma, drain output, and bruising in post-mastectomy breast reconstruction. We will recruit patients undergoing bilateral mastectomy at our institution. Patients will be excluded if they have previous history of bleeding or coagulation disorders. Each patient will serve as their own internal control, with one side receiving saline and the other TXA. During surgery and prior to wound closure, we will moisten the wound surface of one side with 20 cc of dilute TXA 25mg/ml solution, and the contralateral with 20cc of saline. Demographics, cancer details, and surgical characteristics will be collected. Outcomes will we assess include hematoma, seroma, reoperation, drain duration, and degree of ecchymosis will be recorded post-operatively for analysis over a 3-month period. The primary outcome will

be presence of hematoma. Secondary outcomes will include seroma, drain output and duration, ecchymosis, and return to operating room.

The surgeon will mix the TXA solution and pass onto the surgical field (detailed in a later section). After completion of the bilateral mastectomy, the plastic surgeon will perform their portion of the procedure. Immediately prior to final closure, 20ml of 25mg/ml TXA solution will be infiltrated into one breast pocket. 20ml of 0.9% normal saline will be infiltrated into the other breast pocket. No other hemostatic agents will be used. The sidedness of the TXA administration will be documented by the surgery team in our record but kept confidential from the surgery clinic staff to prevent bias at post-operative assessments. The solutions will be allowed to dwell while performing incisional closure, and the solutions will be evacuated by the Jackson-Pratt drain when placed to bulb suction at the end of the case. Post-procedure, each patient will be provided with standard post-operative instructions. They will be followed post-operatively for up to 1 year.

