The surgeon will mix the TXA solution and pass onto the surgical field as outlined above. After the completion of the bilateral mastectomy, the plastic surgeon will perform their portion of the procedure. After obtaining hemostasis and irrigating as per standard practice, they shall not use any other hemostatic agents. Immediately prior to final closure, 20ml of 25mg/ml TXA solution shall be infiltrated into the right breast pocket. 20ml of 0.9% normal saline shall be infiltrated into the left pocket. The sidedness of the TXA administration will be documented by the surgery team in our record but kept confidential from the surgery clinic staff to prevent bias at post-operative assessments. The solutions will be allowed to dwell, and JP drains will be kept off bulb suction until the end of the case. Post-procedure, each patient will be provided with standard post-operative instructions which will include a chart to record drain outputs daily for the right and left sides.

Post-Operative Clinic Visits

Drain output will be assessed at each clinic visit to determine timing for removal. Drains will be removed per standard practice at our institution which is when they have produced < 30cc/day for at least 3 days.

At each clinic visits up to one year after surgery, we will assess for clinical signs of hematoma, seroma, and ecchymoses. The number of post-operative clinic visits and their timings will vary by patient. Patients will be managed for hematoma and seroma as per standard procedure, whether with ultrasound, clinic aspiration, IR drain placement, or return to the operating room as deemed necessary by the senior surgeon.

Optional Segments

If patients have multiple visits within each block of the assessment period (1-4 weeks, 5-11 weeks, and 12 week – 1 year), study-specific assessments and procedures may be performed.

7 Reporting and Documentation of Results

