7.1 Statistical analysis

We will compile an encrypted record of each patient and the study or control solution that was administered to each breast intraoperatively. We will then record data from the condition-specific physical examination at each post-operative clinic visit to track presence of hematoma, presence of seroma, laterality with worse bruising, amount of drain output prior to removal, and number of days with drain prior to removal.

Demographic and surgical details will be collected for each patient. These will include patient demographics (i.e., age, BMI, race, ethnicity), clinical cancer characteristics (i.e., type of cancer, neoadjuvant chemo or radiation, adjuvant chemo or radiation), and post-operative outcomes (i.e., hematoma, seroma, infection, return to the operating room, radiology aspiration or drain placement, clinic aspiration). Results will be analyzed comparing the outcomes of the TXA treated breasts with the Control (Saline) treated breasts using T test for continuous variables, and Chi Squared for categorical variables.

Multivariate regression analysis will also be utilized to assess for the importance of various clinical and demographic factors (BMI, cancer laterality, etc.) on overall outcomes. For ecchymosis, the prevalence of worse ecchymosis with or without TXA will be reported as rated by the provider and patient at post operative visits.

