Appendix 1 (Single Site): Phase II or III Institutional Trial

Data and Safety Monitoring Plan for a Phase II or III Institutional Trial

1. Oversight and Monitoring Plan

The UCSF Helen Diller Family Comprehensive Cancer Center (HDFCCC) Data and Safety Monitoring Committee (DSMC) is responsible for auditing data quality and participant safety for all HDFCCC institutional clinical trials. A summary of DSMC activities for this trial includes:

- Annual auditing (depending on trial accrual)
- Review of serious adverse events
- Minimum of biennial regulatory auditing

2. Monitoring and Reporting Guidelines

Investigators will conduct a continuous review of data and participant safety at monthly site committee meetings where the results of each participant's treatment are discussed and documented in the site committee minutes.

All institutional Phase II and III therapeutic trials are audited on an annual basis, with all data from 20% percent of the enrolled participants audited by the DSMC Monitor/Auditor.

The assigned DSMC Monitor/Auditor will review no more than a total of 10 participant charts during the course of auditing this trial. DSMC Monitor/Auditors will send a follow-up report to the study team within 20 business days after the auditing visit is complete for the PI and the study team to resolve all action items from this report within 20 business days. An abbreviated regulatory review (i.e., reviewing protocol and consent versions, SAEs, PVs, DOA logs, 1572 forms, etc.) will occur at each participant monitoring review; however, a full regulatory review will occur on a biennially basis by the DSMC for regulatory compliance.

Auditing of all enrolled participants in these trials will be complete after 20% of enrolled participants have been audited through five cycles of treatment. However, regulatory reviews of the trial, safety reviews (i.e., Serious Adverse Event (SAE) reviews and Protocol Violation (PV) reviews), and audit/inspection preparation (as applicable) will continue until the trial is closed by the IRB.

3. Review and Oversight Requirements

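### The masking rule covers clinic staff and an undefined observer but makes no provision for the patient, who rates bruising side against side and charts drain output by side

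*Combined protocol and SAP*

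**What the plan says.** Each patient receives TXA in one breast pocket and saline in the other.

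- **Who knows the side.** Section 6.3 states: "The sidedness of the TXA administration will be documented by the surgery team in our record". Sections 3.1 and 6.3 both say that this information is "kept confidential from the surgery clinic staff to prevent bias at post-operative assessments". Section 7.1 says the record of what each breast received is encrypted, without saying who may open it.
- **Bruising.** The first secondary objective in 2.3 is "To evaluate the impact of TXA on patient and provider rating of bruising, comparing the TXA side to the control side". The endpoint cell of the same row says "The observer will be blinded to the laterality of TXA". Section 7.1 will report how often each side was worse, "as rated by the provider and patient at post operative visits".
- **Drain output.** Under 6.3, patients leave with instructions that include "a chart to record drain outputs daily for the right and left sides". In 2.3 the endpoint cell for output counts the drain's whole time in place, but the time frame stops at discharge on the first post-operative day.
- **Which side gets TXA.** Section 6.3 puts TXA in the right pocket and saline in the left. Sections 3.1, 3.6 and 5.1 leave the side open. The 6.1 calendar appears to mark the left breast, although that table may have been disturbed when the text was extracted.
- **Site meetings.** Appendix 1 says "Investigators will conduct a continuous review of data and participant safety at monthly site committee meetings" and that each participant's results are discussed there.

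**The concern.** The plan itself gives the reason for concealment: knowing the side can bias post-operative assessment. It applies that reason to clinic staff, but the patient is an assessor too. A patient who knows which breast had the active drug and is asked which looks worse is giving a directly comparative, subjective answer, and even a slight expectation can tip it when the two sides look alike. Subjective bruising is part of the hypothesis in 2.1 and is listed among the key outcomes in 2.2.

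Drain output is a measured volume, so it is less exposed. However, a patient who reads and writes down two volumes a day can round or record them differently. Drains come out once output has stayed under 30 cc/day for at least 3 days (6.3), so charted values may inform the removal decision and carry some of that error into drain duration.

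If the patient learns the side, the loss of masking cannot be repaired in the analysis.

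**Working it through.** **1. Who assesses, and who is masked**

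| Person | Role in the outcomes | Masking stated |
|---|---|---|
| Surgery team | Applies the solutions, records the side | No; they know it |
| Surgery clinic staff | Post-operative assessments | Yes (3.1, 6.3) |
| Observer of bruising | Compares the two sides | Yes (2.3), but not defined |
| Patient | Rates bruising (2.3, 7.1); charts drain output by side (6.3) | Not stated |

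The only operational step, confidentiality of the side, is directed at clinic staff. The sentence in 2.3 sits in the row that covers both patient and provider ratings, so it could be meant to include the patient, but no procedure carries it that far.

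**2. Whether confidentiality could work as the text stands**

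If 6.3 is followed literally, every patient has TXA on the same side, and anyone who knows that sentence knows the side. This applies to clinic staff as well as patients. Section 3.3 requires that patients be fully informed about the study and makes no exception for the side.

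**3. Which endpoints are reached**

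- Patient bruising rating: directly.
- Drain output: mainly if the endpoint covers the drain's whole time in place. If it ends at discharge on the first post-operative day, a chart handed out with the post-operative instructions contributes little.
- Drain duration: only indirectly, through the charted volumes used to time removal.
- Hematoma and the sample size of 150 per group: not by this route. The plan's figure reproduces: for 5% against 0%, two-sided alpha 0.05 and 80% power, the unpooled normal formula gives 150 per group and the pooled formula 152.

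**4. How sensitive a side-against-side rating is (illustration)**

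The plan gives no figure for this, so the inputs are assumptions: *m* patients give an informative rating (no ties), TXA has no true effect, a share *s* names the saline side as worse through expectation alone, and the rest split evenly.

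Probability of naming saline as worse: π = s + (1 − s)/2 = 0.5 + s/2.

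Shift in the reported prevalence: s/2. For s = 0.10 this is 0.05, or 5 percentage points (a 55:45 split).

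Chance that a two-sided 5% exact sign test is significant: the sum of Binomial(m, π) probabilities over its rejection region. For m = 150 the region is 62 or fewer, or 88 or more. For m = 100 it is 39 or fewer, or 61 or more.

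| s | π | m = 150 | m = 100 |
|---|---|---|---|
| 0 | 0.500 | 4.1% | 3.5% |
| 0.05 | 0.525 | 8.0% | 5.9% |
| 0.10 | 0.550 | 20.7% | 13.5% |
| 0.20 | 0.600 | 66.3% | 46.2% |

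Section 7.1 says only that the prevalence of the worse side will be reported and names no sign test for it. The percentages in the last two columns show sensitivity and are not error rates of this trial. The shift of s/2 applies to the reported prevalence whether or not it is tested.

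**The case against.** The strongest reply is that the documents never say patients are told their side. The side sits in the surgery team's record, the record is encrypted, and consent pages are not in the public copy, so the question may be settled there. The observer sentence in 2.3 may also be meant to cover the patient. All of this is fair. A reader might infer that patients are unmasked by design, and the text does not support that. What stands is that the sections setting out concealment name clinic staff and an undefined observer, and none provides for the patient.

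A reader might also infer that the monthly site meetings breach the confidentiality. Appendix 1 does not say that the side is shown there, or that the clinic assessors attend. It is a possible route, not a demonstrated one, and merits a precaution at most.

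On drains, the reply is that output is measured, removal follows a numeric threshold applied at clinic visits where staff are kept from the side, and the stated time frame for output ends at discharge. This is largely right. It leaves a weaker exposure to recording error and is no ground for calling drain output a subjective endpoint.

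Finally, the rejection rates rest on assumed shares, an unplanned test and a full set of informative ratings. That is accepted, and they are offered only on those terms.

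**Conclusion.** The concern holds in a limited form. Patient masking is not provided for, although the patient is a rater of a subjective, side-by-side endpoint. The bruising rating is the endpoint at real risk. Drain output and drain duration are exposed more weakly, and output mainly under the longer of the two readings in 2.3.

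The size depends on how many patients are swayed, which is unknown. If 10% were, the reported prevalence would move by 5 points, and a sign test on 150 informative ratings would be significant about 21% of the time under a true null (13.5% on 100). These figures rest on the assumptions set out in the working.

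The bruising and drain endpoints are secondary in 2.3 and 3.1, so this does not threaten the primary comparison. It should still be corrected, because the change is small.

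**What to change.** 1. **Sections 3.1 and 6.3.** State that the side is kept confidential from the patient and the surgery clinic staff until the 30-day bruising rating and drain removal on both sides are complete, subject to disclosure where safety requires it.
2. **Section 2.3.** Define the observer so that the patient rater is included.
3. **Sections 3.1, 3.6, 5.1, 6.1 and 6.3.** Reconcile what they say about which side receives TXA. While a fixed side can be read from the protocol, a confidentiality sentence cannot achieve masking, so item 1 depends on this one.
4. **Appendix 1, as a minor precaution.** Present outcomes at site meetings without the side unless safety requires it.

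The cost is a few sentences, one definition and the reconciliation in item 3. This point needs no change to the sample size. The downside is that patients learn their side later.

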3.2 Sample Size

The goal enrollment is 150 patients, 300 breasts. Given that the literature cites a hematoma rate of up to 5% in mastectomy patients, if we aim for complete reduction with TXA, we will need at least 150 per group to be adequately powered to detect that difference (alpha 0.05, beta 0.2). However, since complete reduction is not realistic, we will aim to recruit as many as possible but with a minimum goal of 150 patients (150 breasts will receive TXA, 150 breasts will receive saline).

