1.1 Background on Indication

Post-mastectomy breast reconstruction has significant physical, mental and emotional benefits for breast cancer patients[1]. However hematoma, seroma and bruising are common complications given the highly vascularized nature of breast tissue[2]. These events can compromise the reconstruction, as well as potentially delay cancer treatments including chemotherapy and radiation by predisposing the patient to infection and wound complications. The hematoma and subsequent reoperation rate in breast surgery has been cited from 2-5% [2], thus topical hemostatic agents are often used intraoperatively. However, these agents are usually expensive, come in varying forms, and difficult to regulate. Prior studies in orthopedics, plastic surgery, and trauma have shown a significant reduction in bleeding, ecchymosis, and need for transfusions with use of Tranexamic Acid (TXA)[3-12]. TXA is a synthetic amino acid that blocks plasminogen conversion to plasmin, to prevent fibrinolysis and stabilize clot formation. Improvement in bleeding and bruising has been described utilizing both intravenous and topical off-label applications of TXA[6, 12]. In breast surgery there have been mixed results to preliminary retrospective studies of both intravenous and topical tranexamic acid, with some decreases in hematoma and seroma rates, and drain volumes[13-15]. The proposed prospective trial will evaluate the efficacy of topical TXA in decreasing hematoma and seroma rates, drain output, drain duration, and ecchymosis in bilateral post-mastectomy breast reconstruction patients. Every patient will serve as their own control. This novel use of TXA in breast surgery may provide a simple, cost-effective, and safe way to improve outcomes in breast reconstruction patients.

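### The 150 per group and 80% power reproduce from a normal approximation, but at 5% v 0% the unspecified chi-squared test has exact power of 94.5% or 76.6%, and the plan does not say which version decides hematoma

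*Combined protocol and SAP*

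**What the plan says.** Section 3.1 names presence of hematoma as the primary outcome, and section 3.2 sizes the trial on it alone. (Section 2.2 also lists seroma as primary, but no calculation is given for it.)

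- Control rate: "the literature cites a hematoma rate of up to 5% in mastectomy patients".
- TXA rate: zero, from "if we aim for complete reduction with TXA".
- Error rates and size: "we will need at least 150 per group to be adequately powered to detect that difference (alpha 0.05, beta 0.2".
- Allocation: "150 breasts will receive TXA, 150 breasts will receive saline".

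The Abstract repeats the calculation. Neither place states the formula or whether the test is one- or two-sided. Section 3.2 then qualifies itself: "since complete reduction is not realistic, we will aim to recruit as many as possible but with a minimum goal of 150 patients".

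Section 7.1 says the TXA and saline breasts will be compared "using T test for continuous variables, and Chi Squared for categorical variables". It mentions no continuity correction, exact method or rule for small counts.

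**The concern.** The printed beta of 0.2 is the only power statement in the protocol. It describes a rare event with none expected on one side. With so few events, chi-squared reduces to a count of saline hematomas, and the count needed for significance depends on whether a continuity correction is applied. If the versions differ materially, two things are at stake. The stated power may not describe the test that is run. And the primary conclusion could turn on an analysis choice that is still open when the counts are known.

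**Working it through.** **Inputs.** Saline 5%, TXA 0%, 150 per side, alpha 0.05, power 80% (section 3.2); chi-squared (section 7.1). Two-sided testing is my assumption, since the plan does not say.

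**1. Reproduce the plan's figure.**
- Unpooled variance: n = (1.96 + 0.842)² × 0.05 × 0.95 / 0.05² = 149.1, so 150. Power at 150 is Φ(0.05/√(0.0475/150) − 1.96) = Φ(0.850) = 80.2%.
- Pooled variance: n = (1.96√(2 × 0.025 × 0.975) + 0.842√(0.05 × 0.95))² / 0.05² = 151.9, so 152. Power at 150 is 79.5%.

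The printed figure therefore reproduces.

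**2. Check the approximation.** Expected hematomas are 150 × 0.05 = 7.5 on saline and 0 on TXA. The chi-squared expected count in each event cell is 7.5/2 = 3.75.

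**3. Find the rejection threshold.** With x saline and 0 TXA hematomas in 150 v 150:
- uncorrected chi-squared = 300x/(300 − x)
- continuity-corrected chi-squared = 300(x − 1)²/[x(300 − x)]
- exact McNemar p = 2 × 0.5^x; mid-p McNemar p = 0.5^x. With no TXA events no pair has hematoma on both sides, so only x matters.

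| Split | Uncorrected p | Corrected p | Fisher p | Exact McNemar p | Mid-p McNemar p |
|---|---|---|---|---|---|
| 4 v 0 | 0.044 | 0.131 | 0.122 | 0.125 | 0.0625 |
| 5 v 0 | 0.024 | 0.071 | 0.060 | 0.0625 | 0.031 |
| 6 v 0 | 0.013 | 0.039 | 0.030 | 0.031 | 0.016 |

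**4. Exact power at 150.** This is the probability that X ~ Binomial(150, 0.05) reaches the threshold. The last column is the smallest size per side with exact power of at least 80%.

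| Test | Rejects from | Exact power | Size for 80% |
|---|---|---|---|
| Uncorrected chi-squared | 4 v 0 | 94.5% | 110 |
| Mid-p McNemar | 5 v 0 | 87.4% | 134 |
| Corrected chi-squared, Fisher, exact McNemar | 6 v 0 | 76.6% | 157 |

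**5. How often the two chi-squared versions disagree.** At 5% v 0% they differ when x is 4 or 5: 7.1% + 10.9% = 18.0%. Enumerating all outcomes, with the two sides treated as independent binomials, gives about 14% at 5% v 1% (the 1% is my assumption). It gives about 27% at 2% v 0%, where 2% is the low end of the range in section 1.1.

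**6. Null error.** With a common rate of 2% to 5% and the same independence assumption, the uncorrected test rejects in about 4.4% to 4.8% of trials and the corrected test in 1.2% to 2.4%.

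**The case against.** The strongest reply is that nothing was miscalculated. Uncorrected chi-squared is the square of the pooled two-proportion z statistic, so the standard planning formula for the named test returns 152 and 79.5%, essentially what is printed. The gap comes from asymptotic against exact evaluation of power. Read literally, chi-squared means uncorrected, and then 150 is more than enough for the stated scenario. If corrected, the shortfall is 3.4 points, or 7 more patients (157 v 150), and 150 is only a minimum. The 18% also depends on a TXA rate of exactly zero, which section 3.2 itself calls unrealistic.

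Most of this stands. A reader might infer that the sample size is an arithmetic error, that the trial is underpowered for its own scenario, or that the uncorrected test inflates false positives. The documents do not support any of these: the figure reproduces, the literal reading exceeds 80%, and null error stays below 5%.

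What remains is that neither version of the named test has exact power near the printed 80% at 150, and the plan does not say which version decides the primary outcome. The disagreement does not vanish away from 5% v 0%: it is about 14% at the assumed 5% v 1%.

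**Conclusion.** The point holds as one of specification and of a poor approximation, not as a calculation error. On the plan's own inputs, and assuming two-sided 0.05, exact power at 150 per side is 94.5% or 76.6%, a gap of about 18 points that depends on a choice section 7.1 leaves open. The plan is conservative under one version and slightly short of 80% under the other. In its own scenario, about 18% of trials would be positive under one version and negative under the other.

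This is separate from whether 5% v 0% is a sensible target. Restating power for that scenario does not show what 150 patients can detect if TXA only partly prevents hematoma.

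**What to change.** - **Section 7.1:** before any outcome data are seen, name one two-sided paired small-count test for hematoma. Mid-p McNemar or exact McNemar would serve, and either also fits a design in which each patient is her own control. Exact McNemar guarantees the error rate; mid-p does not by construction, but is less conservative.
- **Section 3.2 and the Abstract:** replace the beta of 0.2 with the chosen test's exact power at 150 pairs for 5% v 0%: 87.4% for mid-p or 76.6% for exact. State that the test is two-sided. Describe 150 as the planned minimum, not as the size that gives 80%.

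**Cost.** These are wording changes, and enrolment does not change. In the 5% v 0% scenario, power is lower than for uncorrected chi-squared by about 7 points (94.5% − 87.4%) with mid-p or about 18 points (94.5% − 76.6%) with the exact test. With the exact test the stated power falls slightly below 80%.

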Sample Size	The goal enrollment is 150 patients undergoing bilateral mastectomy, or 300 breasts. Given that the literature cites a hematoma rate of up to 5% in post mastectomy patients, if we aim for complete reduction with TXA, we will need at least 150 per group to be adequately powered to detect that difference (alpha 0.05, beta 0.2). However, since complete reduction is not realistic, we will aim to recruit as many as possible with a minimum goal of 150 patients, which will give us 300 breasts total such that 150 breasts will receive TXA and 150 breasts saline.
Duration of Study Treatment	Participants will only be treated intraoperatively at the time of surgery with topical TXA to one breast pocket.

Duration of Follow up	We routinely follow post-mastectomy patients up to 1 year after their surgery. The standard post-operative follow-up regimen includes appointments at 1 week, 2 weeks, 6 weeks, 3 months, and 1 year, followed by yearly appointments thereafter. However, the schedule and number of visits will vary by patient. Patients in this study will be assessed at their regularly scheduled visits up to one year post-operatively.
Unique Aspects of this Study	This study is the first in the United States to evaluate the impact of topical Tranexamic Acid on hematoma, seroma, drain output, drain duration, and subjective bruising following post-mastectomy breast reconstruction, utilizing each patient as their own internal control.

List of Abbreviations

AE	Adverse Event
SAE	Serious Adverse Event
DSMC	Data and Safety Monitoring Committee
HDFCCC	Helen Diller Family Comprehensive Cancer Center
HIPAA	Health Insurance Portability and Accountability Act
IRB	Institutional Review Board
IV	intravenous
TXA	Tranexamic Acid

Table of Contents

Protocol Signature Page	2
Abstract	3
List of Abbreviations	5
Table of Contents	Error! Bookmark not defined.
1 Introduction.....	8
1.1 Background on Indication.....	8
1.2 Background on the Investigational Product(s) and Associated Known Toxicities	8
1.3 Rationale for the Proposed Study	9
1.4 Rationale for the TXA Dose Selection/Regimen	9
2 Study Objectives.....	10
2.1 Hypothesis.....	10
2.2 Primary Objective and Endpoint(s).....	10
2.3 Secondary Objective(s) and Endpoint(s).....	11
3 Study Design	11
3.1 Characteristics.....	11
3.2 Sample Size	12
3.3 Eligibility Criteria.....	12
3.3.1 Inclusion Criteria	12
3.3.2 Exclusion Criteria	13
3.4 Inclusion of Women and Minorities	13
3.4.1 Eligibility of Women and Minorities	13

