2.2 Primary Objective and Endpoint(s)

The primary objective of this study is to evaluate the impact of topical TXA versus control (saline) on key post-operative outcome measures. These include hematoma, seroma, drain output, drain duration, bruising, and reoperation.

Primary Objective	Endpoint(s)	Time Frame
1. To evaluate the impact of TXA on hematoma rates compared to control	Presence of hematoma in 30 day period	From application in the operating room to 30 days of follow up
2. To evaluate the impact of TXA on seroma rates compared to control	Presence of seroma in 3 month period	From application in the operating room to 3 months of follow up

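### Section 7.1 plans an unpaired chi-squared test with no interval for a within-patient hematoma comparison that has low power for any partial effect

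*Combined protocol and SAP*

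**What the plan says.** - **Design.** Section 3.1: "Each patient will serve as their own internal control, with one side receiving saline and the other TXA". The same section says that the primary outcome will "be presence of hematoma. Secondary outcomes will include seroma, drain output and duration, ecchymosis, and return to operating room". Section 2.2 lists both hematoma and seroma as primary objectives; the hematoma window runs "From application in the operating room to 30 days of follow up", and the seroma window runs to 3 months.
- **Sample size.** Section 3.2: "if we aim for complete reduction with TXA, we will need at least 150 per group to be adequately powered", at alpha 0.05 and beta 0.2, from a hematoma rate of up to 5%. It then concedes the point: "since complete reduction is not realistic, we will aim to recruit as many as possible but with a minimum goal of 150 patients". The abstract says nearly the same: "since complete reduction is not realistic, we will aim to recruit as many as possible with a minimum goal of 150 patients". Section 1.1 gives a range: "The hematoma and subsequent reoperation rate in breast surgery has been cited from 2-5" per cent.
- **Analysis.** Section 7.1 compares TXA-treated with saline-treated breasts by t test for continuous outcomes and chi-squared for categorical ones, plus a multivariate regression. It names no paired method and no interval.
- **Timing.** Sections 3.8 and 3.9 put primary completion and study completion at the same point, 2 years after opening to accrual. Section 3.8 expects at least 150 participants within those 2 years.

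**The concern.** The design's main strength is that each patient is her own control, and the planned test does not use it. An ordinary chi-squared test treats the 300 breasts as independent. If a patient who bleeds on one side is more likely to bleed on the other, the test uses too large a variance. Its real error rate is then not the nominal one, and the benefit of pairing is lost.

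The second issue is how the result will be read. The only effect with stated power is one that the protocol calls unrealistic. For a partial effect the likeliest outcome is a non-significant test. Without an interval, that could be taken as evidence that TXA does not work, when the data may fit anything from no effect to removal of all hematomas.

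**Working it through.** **Inputs.** Alpha 0.05, beta 0.2, rates 5% and 0%, 150 pairs (3.2); range 2% to 5% (1.1). Assumed, because not stated: two-sided test, no dropout, 5% taken as a per-breast rate, within-patient correlation φ from 0 to 0.3.

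**1. The plan's own figure.**
- Unpooled: n = (1.960 + 0.842)² × 0.05 × 0.95 / 0.05² = 149.1.
- Pooled: n = [1.960 × √(2 × 0.025 × 0.975) + 0.842 × √(0.05 × 0.95)]² / 0.05² = 151.9.

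The stated 150 reproduces as an unpaired normal-formula figure.

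**2. Size of the unpaired test.** With equal rates p on both sides, the test uses variance 2p(1−p)/n, but the true variance of the difference is 2p(1−p)(1−φ)/n. At φ = 0.3 the true size is about 2 × [1 − Φ(1.960/√0.7)] = 2 × [1 − Φ(2.343)] = 1.9%. Full enumeration at 150 pairs agrees:

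| Equal rates | φ | Uncorrected chi-squared | Mid-p McNemar |
|---|---|---|---|
| 5% | 0 | 4.8% | 4.5% |
| 5% | 0.3 | 1.9% | 4.1% |
| 2% | 0 | 4.6% | 3.0% |
| 2% | 0.3 | 1.9% | 1.8% |

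At 5% the mid-p test stays near nominal whatever φ is. At 2% it is itself conservative, because events are so few.

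**3. Power at 150 pairs, independent sides.** Cell probabilities are p11 = pc·pt + φ√[pc(1−pc)pt(1−pt)], p10 = pc − p11 and p01 = pt − p11, where pc is the saline rate and pt the TXA rate. Outcomes are enumerated over the multinomial.

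| Saline v TXA | Chi-squared, uncorrected | Chi-squared, Yates | Exact McNemar | Mid-p McNemar |
|---|---|---|---|---|
| 5% v 0% | 95% | 77% | 77% | 87% |
| 5% v 1% | 54% | 40% | 40% | 52% |
| 5% v 2.5% | 20% | 12% | 13% | 18% |
| 2% v 0% | 35% | 8% | 8% | 18% |

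Hand checks:
- With a TXA rate of 0%, φ cannot matter. Mid-p rejects at 5 v 0 discordant pairs (0.5⁵ = 0.031) but not at 4 v 0 (0.0625), so its power is P(X ≥ 5). For Bin(150, 0.05) that is 0.874; for Bin(150, 0.02), 0.183. Exact McNemar needs 6 v 0 (2 × 0.5⁶ = 0.031), and P(X ≥ 6) = 0.766 at 5%.
- For halving, the unpaired normal formula gives Φ[(0.025√150 − 1.960 × 0.2687)/0.2681] = Φ(−0.82) = 20.5%.

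At φ = 0.3, power for halving is 15% with uncorrected chi-squared and 23% with mid-p McNemar.

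**4. If 5% is a per-patient rate.** Section 3.2 words it as a rate in mastectomy patients. The per-breast rate would then be nearer 2.5%. Mid-p power for 2.5% v 0% is P(X ≥ 5) for Bin(150, 0.025) = 0.322, about 32%.

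**5. What an interval shows.** Take 8 saline-only and 4 TXA-only hematomas in 150 pairs, with none on both sides. The difference is (8 − 4)/150 = 2.7 points, with a Tango 95% interval of −2.1 to 7.9. Exact McNemar p = 0.388; mid-p = 0.388 − 495/4096 = 0.27. The interval covers both no effect and removal of the whole saline-side rate (8/150 = 5.3%).

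**6. Dates.** If 150 patients accrue evenly over 2 years (assumption), those with unfinished windows at that date number 150/730 × 30 = 6 for 30 days, 150/24 × 3 = 19 for 3 months and 150/24 × 12 = 75 for one year.

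**The case against.** **The limit is disclosed.** This stands. The protocol says its own scenario is not realistic. Halving is this review's illustration; the documents name no partial effect. A missing power table would not be much of a finding on its own. It matters here because no interval is planned either.

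**The chi-squared test is adequate, even stronger.** This stands in part. With independent sides the uncorrected test holds its size (4.6% to 4.8%) and has more power than mid-p McNemar: 95% v 87% for 5% v 0%, and 20% v 18% for halving. But its size depends on an unknown correlation, and at 0.3 the order for halving reverses (15% v 23%). Section 7.1 also does not say whether a continuity correction applies; with one, power for 5% v 0% is 77%, below the planned 80%. The chi-squared named there might be meant as McNemar's, but nothing in the text says so.

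**Stronger readings that a reader might infer.**
- *The sample size is miscalculated.* It is not; it reproduces.
- *The unpaired test inflates false positives.* With positive correlation the error is in the conservative direction.
- *Open-ended recruitment inflates type I error.* The documents do not show this. Section 3.2 has a goal of 150, section 3.8 a 2-year forecast, and no interim efficacy test is planned. Section 3.1 also says that sidedness is "kept confidential from the surgery clinic staff to prevent bias at post-operative assessments". Little weight should rest on that, because section 6.3 names one fixed side for TXA, which is a separate matter to reconcile.
- *The trial must be enlarged.* The plan never claims power for a partial effect, so this does not follow.

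**Conclusion.** The point holds as an analysis fault with a reporting gap. A within-patient design is to be analysed with an unpaired test whose true size runs from about 5% down to about 2% as the correlation goes from 0 to an assumed 0.3. No interval is planned, although power for halving a 5% rate is about 12% to 20% with independent sides, depending on the test. These figures assume a two-sided test, no dropout and a per-breast rate of 5%; if the rate is per patient, power is lower. The basis of 150 is arithmetically sound and its limit is disclosed. No bias from the lack of a fixed accrual close is shown. The shared 2-year date in 3.8 and 3.9 is a minor inconsistency with the outcome windows and with follow-up of up to one year.

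**What to change.** 1. **Section 7.1.** Replace the chi-squared test for hematoma with: *Hematoma within 30 days is analysed as paired data: two-sided mid-p McNemar test at 0.05, which decides significance, and the paired risk difference (saline minus TXA) with a 95% Tango score interval, reported whatever the p-value.* Use the same paired approach for seroma. Mid-p is preferred to exact McNemar because the exact test would put the plan's own 5% v 0% case at 77%, under its stated 80%.
2. **Section 3.2 and abstract.** Keep the 5% v 0% basis and say that it is an unpaired normal-formula figure. Add: *Taking 5% as a per-breast rate with independent sides, 150 pairs with the mid-p McNemar test give about 87% power for 5% v 0%, 52% for 5% v 1%, 18% for 5% v 2.5% and 18% for 2% v 0%. If 5% is a per-patient rate, the per-breast rate and the power are lower (2.5% v 0%: about 32%).*
3. **Sections 3.8 and 3.9 (minor).** Set primary completion after the last patient's 30-day and 3-month windows, and reconcile study completion with the one-year follow-up in 3.1, 3.7 and 6.1. Stating an accrual close that does not depend on outcomes is sensible but secondary.

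Make the change by amendment before any comparison by treated side. **Cost:** wording and minor analysis work, with no added visits or patients. The stated power for partial effects will look less favourable, and if the sides prove independent the paired test gives up a little power against an uncorrected chi-squared.
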